Advocating for Supports to Improve Service Transitions (ASSIST)

NCT04173663

Statistical Analysis Plan

Document Date: 06/01/2022

STATISTICAL DESIGN AND POWER

Effects of the Intervention: Aims 1 and 2: Generalized linear models will be used to estimate the effect of treatment group assignment on each of the outcome variables considered. All models will include an indicator variable for treatment group and a treatment by time interaction while controlling for site and sex to improve the precision of the treatment effect estimate. We choose to model site as a fixed effect (2 d.f.) rather than a random effect because there are too few sites to have a stable estimate of a random effects variance.

For **Aim 1**, continuous outcomes (empowerment, advocacy skills, advocacy activities) will be modeled using linear regression and ordinal outcomes (knowledge) will be modeled using proportional odds ordinal logistic regression. The proportional odds model generalizes the non-parametric Wilcoxon rank sum test to a regression setting and is applicable to a wide variety of outcome types. However, we will consider parametric models for count data including Poisson and Negative Binomial regression if appropriate. In these cases, sensitivity analyses will be conducted to evaluate if our conclusions are robust to the choice of regression model.

The general analysis plan for **Aim 2** will be identical to Aim 1, except indicators of youth outcomes will be considered. Continuous outcomes (e.g., social participation) will be modeled using linear regression, binary outcome (e.g., employment/PSE) will be modeled using logistic regression, and ordinal outcomes (e.g., number of services) will be modeled using proportional odds ordinal logistic regression (or another model, as specified in Aim 1). Time since beginning the VAP-T workshop will be the time scale of interest for all subjects, and we will flexibly model changes over time using restricted cubic splines. Significant changes over time will be assessed using likelihood ratios tests. For continuous outcomes, we will fit separate linear mixed effects models that include a random intercept to account for correlation arising from taking repeated measurements on the same subject over time. In sensitivity analyses we will use the Akaike Information Criterion to compare different models of the longitudinal correlation (e.g. random intercept, autoregressive, unstructured). For binary and ordinal longitudinal outcomes, we will use generalized estimating equations (GEE) and the robust Huber-White sandwich estimator clustering on participant identifier to account for longitudinal correlation. Analyses for Exploratory Aims 2a (using data collected from youth with ASD) and 2b (examining maintenance of treatment effects) will follow this same approach.

Aim 3: While evaluating the main effects of interventions is critical to improving outcomes, it is also important to examine mediators of randomized-controlled trials – even those that are unsuccessful – in order to determine how interventions may work^{84,85}. Examining mediators will provide evidence for the mechanisms of change, offering direction for program implementation and future research⁸⁶. To assess direct and indirect effects of potential mediator variables, we will follow the steps outlined by MacKinnon and colleagues^{79,80} to establish mediation. Regression models will be specified to preserve temporal ordering by considering covariates collected at the prior wave and outcomes collected at the current wave. Model-based causal mediation analysis will be proceeded in two steps: (1) specifying the mediator model for the conditional distribution of the mediator given treatment and pre-treatment covariates and (2) specifying the outcome model for the conditional distribution of the outcome given treatment, the mediator, and covariates. Models will be estimated using the mediation package in R which allows for linear, logistic, ordinal, and generalized linear statistical models for both the mediator and outcome models⁸¹. Bootstrapping will be used to estimate a non-parametric 95% confidence interval for the indirect effect. The indirect effect will be statistically significant if the confidence interval does not contain 0. We will conduct sensitivity analyses to evaluate the sequential ignorability assumption, which is also available in the mediation package in R. Furthermore, we will consider sensitivity analyses using structural equations models, and multivariable models adjusting for potential confounders will be used to confirm any findings.

Exploratory Aim 4: The starting point for multivariable modeling is an additive effects model. A purely additive model, even one with allowance for flexible nonlinear relationships, will not fit adequately if interactive or synergistic effects exist. Empirical search for interactions is unreliable because there are too many possible interactions (product terms) and frequently interactions found by intensive search techniques are spurious. Instead, interactions will be pre-specified based on subject matter knowledge and all results reported, regardless of statistical significance. Separate models will be fit for each moderator by including an interaction between the potential moderator and the treatment by time interaction. A similar model fitting strategy as outlined for Aim 1 and Aim 2 will be followed.

Though we are interested in examining the potential role of race/ethnicity as a modifier, it may be difficult to disentangle the effects of race/ethnicity from study site (as the geographic area of each site has a different racial/ethnic make-up). We will examine cross tabulation tables of the association between race/ethnicity and

site to determine how strongly they are associated. If possible, we will examine race/ethnicity as a moderator.

We will present any race/ethnicity results cautiously and clearly indicate the associations with site that could confound the observed associations.

As part of Aim 4, we will also use qualitative data analysis to code information gained from the open-ended questions regarding ways to adapt the intervention for youth with ASD. All interviews will be recorded and transcribed verbatim. With Atlas-TI, emergent coding⁸⁷ and constant comparative analysis will be used to identify themes in the transcripts⁸⁸.

Missing Data. An advantage to our proposed random effects longitudinal models is that they will readily incorporate both missing waves of data and mistimed measurements. In general, we will assume that data are missing-at-random (MAR) for the growth models and missing completely at random (MCAR) for binary and ordinal outcome models estimated using GEE and mediation analysis. Attrition analysis will be used to evaluate these assumptions. Analysis methods will also consider subjects who fail to complete the study (“dropouts”). Indirect information about the dropouts will be obtained by using binary logistic models to predict the probability of dropping out on the basis of all baseline predictor variables. When a variable is a significant predictor of dropout, the distribution of that variable differs for completers and subjects who drop out.

Power/Sample Size: We plan to recruit 180 subjects and after dropout expect to retain 162 subjects through initial post-test (Aim 1) and 152 subjects (76 per treatment group) through the 12-month follow-up (Aims 2 - 4). For power calculations, we consider baseline to post-test changes using the smaller sample size of 152. For continuous outcomes, the size of effect that we will have 80% power to detect will be impacted by the correlation between the pre and post measurement of the outcome. At worst ($r=0$), we will have 80% power to detect a 0.46 sd difference in continuous outcomes. If the correlation is 0.2 or 0.4, we will be able to detect a 0.29 or 0.17 sd difference, respectively. We believe these estimates are conservative because, from our pilot work, correlations between baseline and post-test scores of intervention targets were 0.56 (empowerment), 0.39 (advocacy skills), and 0.57 (knowledge). For binary outcomes, in pilot data, the probability of being employed or in PSE was about 0.5, so under this assumption we will have 80% power to detect a relative risk of 1.44. Regarding Aim 4, we will have 80% power to detect a 0.42 sd modification of the treatment effect assuming a $r=0.2$. All calculations assume a two-sided significance level of 0.05.

The power to detect mediation effects were made using the MedPow package in R^{82,83}. For the power calculation, we considered moderate associations between (1) VAP-T and the mediator ($r_{X,M}=0.3$), (2) Mediator and outcome, controlling for VAP-T ($r_{M,Y|X}=0.25$), (3) VAP-T and the outcome controlling for the mediator ($(r_{X,Y|M}=0.1)$ using a fixed sample size of 152 ($\alpha=0.05$). Under these assumptions, we have 83% power to detect the indirect effect of VAP-T on the outcome through the mediator.

Additional Analyses. In addition to these key analyses, we will conduct descriptive analyses to inform future research and development of the VAP-T. For example, we will carefully examine the attendance data to determine whether there is a number of sessions that seems necessary to benefit from the VAP-T, whether any particular sessions seem to be more important, and if accessing a greater proportion of sessions outside of the group format (i.e., at home, online) limits effectiveness. Analyses will include (but not be limited to) examining frequencies, medians, and means on intervention target scores for those who attended (vs. missed) each session and examining the distribution of outcome variables by the number of sessions in which content was accessed in the group format and by any format (in-person and online combined). We will also perform variable clustering and redundancy analysis by examining the correlation among the potential attendance predictors. We will work closely with our biostatistician to identify appropriate inferential statistics if these initial analyses appear informative to the further development of the VAP-T program.

BIBLIOGRAPHY

82. Cohen J. *Statistical power analysis for the behavioral sciences*. 2nd ed. Hillsdale, N.J.: L. Erlbaum Associates; 1988.

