Effects of the Intervention (Aims 1 and 2): Generalized linear models accounting for repeated measurements over time will be used to estimate the effect of treatment group assignment on each of the outcomes. In modeling, outcomes will be considered at their key time-points with treatment group and the interaction of treatment with time serving as the main explanatory variables. Such a model will allow us to test for differences between treatment and control groups over time while accounting for heterogeneity among subjects at baseline. While the randomized block design should minimize confounding, we will adjust for site and sex to improve precision. Regarding the choice of statistical model, we will use ordinary multiple regression for truly continuous responses, logistic regression for binary responses, and for outcome scales that are not truly continuous or have heavy ties in some of their values, the proportional odds ordinal logistic model. The error structure of the model is assumed to be compound symmetric, and the validity of this assumption will be examined by computing Akaike Information Criteria against other common structures. **Mediation (Aim 3):** To assess direct and indirect effects of potential mediator variables, we will follow steps outlined by MacKinnon and

colleagues to establish mediation. Mediation models will be estimated using the “mediation” package in R. **Moderation (Exploratory Aim 4):** Modifiers of treatment effect over time will be considered by introducing interactions between modifiers and the treatment by time interaction. The model building and validation strategy will otherwise be the same as for Aims 1 and 2.

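### The Aim 1 and 2 models name no treatment contrast or visit and give the baseline score no stated role, which can cost precision

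*SAP*

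**What the plan says.** The SAP (Effects of the Intervention: Aims 1 and 2) gives the terms common to every model: "All models will include an indicator variable for treatment group and a treatment by time interaction while controlling for site and sex". For Aim 1, "continuous outcomes (empowerment, advocacy skills, advocacy activities) will be modeled using linear regression". For repeated continuous outcomes, "we will fit separate linear mixed effects models that include a random intercept to account for correlation arising from taking repeated measurements". Binary and ordinal outcomes go to GEE with a robust variance. Time runs from the start of the workshop, and "we will flexibly model changes over time using restricted cubic splines". The one test named is this: "Significant changes over time will be assessed using likelihood ratios tests".

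Protocol section 8 makes both treatment and treatment-by-time the main explanatory variables. It says the model will "test for differences between treatment and control groups over time while accounting for heterogeneity among subjects at baseline" and that "we will adjust for site and sex to improve precision".

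The SAP's Power/Sample Size text bases its figures on change from baseline to post-test in 152 families, 76 per arm. It gives a detectable difference of 0.46 sd at r = 0 as the worst case, 0.29 sd at r = 0.2 and 0.17 sd at r = 0.4. Pilot correlations are 0.56 (empowerment), 0.39 (advocacy skills) and 0.57 (knowledge). Randomisation (Protocol section 4) is blocked within site on intellectual disability (ID) and high-school status.

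**The concern.** A model with a treatment term and a treatment-by-time term contains several possible treatment effects: the arm difference at a given visit, the difference in change from baseline, the arm difference at time 0, an average over visits, or a joint test of both terms. The plan does not choose. It also does not say whether T0 enters as a response, as a covariate or not at all, and that decides what each coefficient means.

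Two things are at stake. First, precision: a visit difference ignores a baseline score that was collected before randomisation, and a change score uses it with a fixed weight of one. Regression on baseline is at least as precise as either. Second, the estimand: if T0 is a response, some coefficients of the stated model do not measure the effect after training.

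**Working it through.** **Inputs.** 76 per arm, two-sided 0.05 and 80% power (SAP, Power/Sample Size); r = 0.39 for advocacy skills and r = 0.56 for empowerment (same text). Outcomes are scaled to sd 1, with the same sd at both visits. Knowledge is left out because the SAP models it as ordinal.

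**The plan's own figures.** One-visit comparison: (1.960 + 0.842) × √(2/76) = 0.454 sd by the normal formula, 0.457 by noncentral t. This reproduces the stated 0.46. For the binary outcome, 0.50 × 1.44 = 0.72, and 0.50 against 0.72 with 76 per arm has power 0.800, which is again a comparison at one visit.

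**Variance factors.** Visit difference 1; difference in change 2(1 − r); baseline-adjusted 1 − r². The detectable difference is 0.457 × √factor.

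**Does any reading match the power text?**

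| r | SAP states | Visit | Change | Adjusted |
|---|---|---|---|---|
| 0 | 0.46 | 0.457 | 0.647 | 0.457 |
| 0.2 | 0.29 | 0.457 | 0.579 | 0.448 |
| 0.4 | 0.17 | 0.457 | 0.501 | 0.419 |

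A visit difference does not depend on r. A change contrast starts at 0.647, not 0.46. Of the three, only baseline adjustment starts at 0.46 and falls with r, and it does not reach 0.29 or 0.17.

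**At the pilot correlations.**

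| Outcome | Quantity | Adjusted | Visit | Change |
|---|---|---|---|---|
| Skills, r = 0.39 | factor | 0.848 | 1 | 1.220 |
| | detectable, sd | 0.421 | 0.457 | 0.505 |
| | power at 0.46 sd | 0.864 | 0.804 | 0.723 |
| Empowerment, r = 0.56 | factor | 0.686 | 1 | 0.880 |
| | detectable, sd | 0.379 | 0.457 | 0.429 |
| | power at 0.46 sd | 0.925 | 0.804 | 0.852 |

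**In families, out of 152.** Against a visit difference the loss is 152r²: 23 (skills) and 48 (empowerment). Against a change contrast it is 152 × [1 − (1 − r²)/(2(1 − r))] = 76(1 − r): 46 and 33. The change figures treat baseline and one follow-up as separate time points. With smooth time the loss depends on the curve. For empowerment, assuming visits at 0, 3, 15, 21 and 33 months and compound symmetry, it is about 20 to 31 families with linear or three-knot spline time.

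**What other coefficients would estimate if T0 is a response.** Take a true post-training effect of 0.46 sd. The treatment coefficient at time 0 is the arm difference before training, so it estimates 0. An average over T0 and post-test estimates (0 + 0.46)/2 = 0.23. With k visits and a constant effect, the average is (k − 1)/k of the truth.

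**The case against.** The strongest reply is that baseline adjustment may be what the authors meant. The power text says the detectable effect depends on the pre-post correlation and is worst at zero, and the protocol claims to account for differences among subjects at baseline. If so, there is no loss, only a model description that does not match the power section. This stands as a possibility. It does not settle the matter, because no model term carries it out and the 0.29 and 0.17 sd figures fit none of the three formulas.

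A second reply is that a random-intercept model with T0 among the responses already uses baseline. This also stands in part. A reader might infer that the plan ignores baseline data; the documents do not support that, since they leave T0's role open. But with a free treatment main effect and two visits, the interaction is then the difference in change, which is less precise than adjustment at both pilot correlations.

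A third reply is that treatment and its interaction could be tested jointly over several visits. With T0, post-test and 12 months, a sustained 0.46 sd effect, separate time points and compound symmetry (all assumed), that test has power 0.91 (skills) and 0.95 (empowerment), against 0.94 and 0.97 for the matching adjusted test. On that reading the loss is small.

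**Conclusion.** The gap is real. The plan names no treatment contrast or visit and gives baseline no stated role, and on either single-contrast reading it does not match its own power text. For the two continuous targets with a pilot correlation, baseline adjustment raises power at 0.46 sd from 0.80 or 0.72 to 0.86 (skills), and from 0.80 or 0.85 to 0.93 (empowerment). These figures assume complete data on 76 per arm, equal sds and correlations as in the pilot.

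Three stronger readings go too far:

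- **That the primary outcomes are underpowered.** The protocol's outcome key marks empowerment and skills as intervention targets. No baseline correlation is given for a primary outcome, so the gain there cannot be computed and may be small.
- **That the omission biases the result, or that it never can.** With complete data, a visit or change contrast is unbiased under randomisation and loses only precision. A time-0 coefficient, or an average that includes T0, would miss the post-training effect, but nothing says either will be reported. Bias in the GEE outcomes through dropout would need dropout to depend on baseline differently by arm, and the documents give no such data.
- **That the type I error is inflated.** That needs the contrast to be chosen after seeing results, which the documents do not say.

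This should be corrected, but it does not invalidate the design.

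**What to change.** - **Contrast.** For each outcome, name one contrast and the visit: post-test for the Aim 1 targets, 6 and 12 months for Aim 2. The visit must be one at which the instrument is collected. In the protocol's measures table, advocacy activities has no post-test assessment and is marked primary at 12 months.
- **Continuous outcomes.** Either use the baseline score as a covariate with post-baseline visits as responses, or keep T0 as a response and constrain the arms to a common baseline mean.
- **Binary and ordinal outcomes.** Where baseline is meaningful, add it as a covariate. Goal attainment has no baseline value, because that visit only identifies the goals. Use Wald or score tests under GEE, which has no ordinary likelihood ratio test, and say which odds ratio is reported.
- **Blocking factors.** Add ID and high-school status, as recorded at baseline, to site and sex. The gain is small: about 0.3 to 2.5 power points in a baseline-adjusted model if they explain an assumed 5 to 20% of variance.
- **Timing.** Record when the change was made relative to access to outcome data by arm. The last cohort 2 intervention group finished in February 2021, so 12-month follow-up fell due about February 2022. Read month first, the SAP date of 06/01/2022 is later than that.
- **Sensitivity analysis.** Report the model as now written, with its contrast named.

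The cost is a few sentences and a few degrees of freedom. Odds ratios for binary and ordinal outcomes become conditional on more covariates.

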3. **Expanded Outcomes.** In the VAP-T, we move beyond an emphasis on competitive employment, and instead focus on an expanded list of outcomes. These include access to needed services in PSE, health, financial support, housing, employment, and self-determination, which in turn foster fulfilling day-to-day activities and greater community engagement. Such an expanded – but specific – sense of adult success is rarely if ever included in intervention studies.
4. **Formal and Informal Supports.** We adopt a larger sense of services and resources, including but going beyond formal service systems. In most states, adult services are under-funded and fragmented. Thus, while we provide knowledge about various services, agencies, eligibility requirements, and other

issues, we also provide parents with information about additional resources – everything from disability-related call lines and parent groups, to names of local businesses amenable to hiring young adults with ASD. By expanding the focus to both formal and informal resources, we increase the likelihood that ASSIST can be broadly implemented, to areas with and without abundant adult services.

5. **More Nuanced Understandings of Treatment Effects.** The service needs of adults with ASD differ based on their personal characteristics and other factors such as stage of life. In keeping with the recommendation of Hoagwood et al., we will examine a limited number of targeted moderators of treatment response. We will assess the degree to which parents of offspring with different intellectual abilities benefit from ASSIST, and whether benefits depend on if the youth is in or out of high school. This will provide important evidence to suggest who might benefit most from the ASSIST program, as well as insight into how the program might be adapted to better serve those who are less responsive to ASSIST.

3. Inclusion/Exclusion Criteria

The goal of this study is to arrive at a sample of 180 families (one parent and one youth with ASD per family). We will recruit 2 cohorts of 90 families per cohort. Each of the three sites will recruit and test participants over the course of the study:

- Vanderbilt University Medical Center: n=60 (cohort 1 n=30, cohort 2 n=30)
- University of Wisconsin-Madison: n=60 (cohort 1 n=30, cohort 2 n=30)
- University of Illinois at Urbana-Champaign: n=60 (cohort 1 n=30, cohort 2 n=30)

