After eligibility is determined and baseline data are collected, parents will be randomized, in two cohorts, to the treatment or materials-only control condition. Given the relatively small sample size in each cohort at each site ($n = 30$ at each of three sites), simple randomization is not recommended as it might result in unequal group sizes. We will use 1:1 block randomization within each site to give an equal number of subjects in each group. To ensure balance of important covariates, we will block on our key moderators: whether the youth has an intellectual disability (ID) and is in high school. Co-occurring ID and being in vs. out of high school impact service eligibility, and ID impacts the likelihood of PSE and community employment. By balancing moderators, we maximize our power to detect effect modification of the treatment effect; and we minimize the chance of having a very extreme distribution of important (moderating) covariates.

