1.0 Study Procedures

All data collection will occur in years 2019-2023 as explained below:

- Enrollment for the project is expected to occur in years 1-2.
- Cohort 1 (C1) Intervention group will take ASSIST from February-August 2020 (IL and TN sites; includes COVID break) and August-November 2020 (WI sites)

- C1 Control group will take ASSIST September-November 2021 (TN and IL Sites) and January-March 2022 (WI Site)
- Cohort 2 (C2) Intervention group will take ASSIST from August-Nov 2020 (TN and IL Sites) and November 2020-February 2021 (WI site)
 - C2 control group will take ASSIST from February-April 2022 (TN and IL) and March-May 2022 (WI sites).

Note: Due to social distancing restrictions, the in-person intervention series that began in February 2020 was paused between Spring 2020 to Summer 2020 for Cohort 1 intervention groups (TN and IL). In response to continued pandemic regulations, ASSIST was moved to synchronous web-conferencing in Summer 2020, and this method was the mode of delivery for all remaining sessions and series at all sites (TN, IL, WI)

A comprehensive characterization of each participant's circumstances and family context will be completed by administering a battery of direct assessments and informant report measures during the baseline visit. This visit will include structured observations, psychological testing, structured interviews, and questionnaires/surveys. Note that some of the survey measures will be offered to participants as web-links to be filled out at home or at the lab if social distancing restrictions allow. Paper copies of all surveys will be available based on participant preference.

Follow-up data collection points (post-intervention, 6, 12, 18, 24, and 30 months) may take place online or over the phone, depending on participants' preference and the included measures to be collected for that time-point. We will also make alternate methods of data collection available to youth with ASD for the interview, including video/text/online chat, as some participants with ASD may be more comfortable answering questions via chat than over the phone or web conference. The table of measures included in the *Procedures for Enrolled Families* section of this protocol, shows the longitudinal measures follow-up schedule for parent and youth participants.

5. Procedures

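### The Aim 1, 2, 2a and 2b models omit the site-by-cohort series that families are randomised in, and give the one third interrupted by the shutdown the same time curve as the rest; the cost is modest precision.

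*SAP*

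**What the plan says.** **Allocation.** Under Randomization, Protocol section 4 states that "parents will be randomized, in two cohorts, to the treatment or materials-only control condition". It adds: "We will use 1:1 block randomization within each site to give an equal number of subjects in each group". The reason given for blocking is that each site has only 30 families per cohort. Section 3 sets the sizes: "We will recruit 2 cohorts of 90 families per cohort", with 30 per site in each.

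**Calendar.** The Study Procedures section gives the workshop dates of the intervention groups. Tennessee and Illinois cohort 1 ran from February to August 2020, and the note there says that "the in-person intervention series that began in February 2020 was paused between Spring 2020 to Summer 2020 for Cohort 1 intervention groups". Wisconsin cohort 1, and cohort 2 in Tennessee and Illinois, ran from August to November 2020. Wisconsin cohort 2 ran from November 2020 to February 2021.

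**Models.** The SAP, under Effects of the Intervention, includes treatment and "a treatment by time interaction while controlling for site and sex to improve the precision of the treatment effect estimate", with site as a fixed effect on 2 d.f. Protocol section 8 agrees: "we will adjust for site and sex to improve precision". Time is measured from the start of the workshop for everyone and modelled with restricted cubic splines. Continuous outcomes get a random intercept; binary and ordinal outcomes use GEE with robust errors. Aims 2a and 2b take the same approach. The SAP is dated June 2022 and names no cohort, calendar or pandemic term in these models.

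**The concern.** The site-by-cohort series is a feature of the allocation, known for every family before randomisation. The plan adjusts for site to gain precision, and the same reason applies to series.

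The series are unlikely to share a time course. Baseline precedes randomisation, so the baselines of Tennessee and Illinois cohort 1 predate February 2020 and their follow-up falls inside the pandemic. For these families, change from baseline in employment, post-secondary education, services or social participation runs from before the shutdown into it; for the other series that start is unlikely or unclear. The time axis differs too. A 12-week programme took about six months in the two early series and about three elsewhere, so the end of the workshop falls near month 6 in one group and near month 3 in the other. A curve shared by all series within an arm merges the two.

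At stake is residual variation that a known factor could remove. There is also some exposure to dropout, since any imbalance in series mix among retained families would let the series trend into the treatment-by-time estimate.

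**Working it through.** **Inputs.** 180 families, 60 of them in the two early series (Protocol section 3 and Study Procedures). 152 retained at 12 months, 76 per arm, so 14 of 90 lost per arm (SAP, Power/Sample Size). Two-sided alpha 0.05. The documents give no difference in change between series, so *d* = 0.3, 0.5 and 0.8 SD is an assumed range, in units of the within-series SD of change.

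**1. The plan's own figure.** Detectable difference at 80% power = (1.960 + 0.842) × √(2/76) = 0.454 SD (0.457 with the t distribution). The stated 0.46 SD reproduces.

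**2. Precision.** A shift *d* between one third of families and the rest adds variance *d*² × (1/3)(2/3). The last column takes the plan's SD as the total SD and multiplies 0.454 by the SE ratio.

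| *d* | added variance | SE with term ÷ SE without | equivalent extra families of 152 | detectable difference with term |
|---|---|---|---|---|
| 0.3 | 0.020 | 1/√1.020 = 0.990 | 3 | 0.450 |
| 0.5 | 0.056 | 1/√1.056 = 0.973 | 8 | 0.442 |
| 0.8 | 0.142 | 1/√1.142 = 0.936 | 22 | 0.425 |

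The standard error falls by about 1%, 3% and 6%. Read the other way, leaving the term out makes it about 1%, 3% and 7% larger.

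**3. Validity with complete data.** Balance within series means that the shift cancels in the treatment contrast but stays in the residual variance, so the reported SE is too large. Null rejection is 2 × [1 − Φ(1.96 × √(1 + 2*d*²/9))] = 0.048, 0.044 and 0.036. A simulation with a 50:50 split (20,000 runs per setting, pre-post correlation 0.4, *d* = 0.2, 0.5, 0.8 in outcome SDs) gave 0.048, 0.045 and 0.039 with no bias, and about 0.05 once the factor was fitted.

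**4. Bias under differential loss.** Bias = *d* × (difference between arms in the early-series share among those retained).

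- Loss unrelated to series, or related to it equally in both arms: zero.
- One arm loses 9 of its 30 early-series families and the other loses 1. The shares are 21/76 and 29/76, a gap of 8/76 = 0.105. Bias is 0.03, 0.05 and 0.08 SD.
- The limit: all 14 losses in one arm from the early series, and none in the other. The gap is 14/76 = 0.184. Bias is 0.06, 0.09 and 0.15 SD.

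**5. How likely such a gap is by chance.** If loss is unrelated to series, the number of early-series families lost per arm is hypergeometric, with variance 14 × (1/3)(2/3) × (76/89) = 2.66. The SD of the difference between arms is √5.31 = 2.3 families. A difference of 8 or more in either direction has probability of about 0.001.

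This arithmetic is for a continuous change score and is only a guide for the logistic and ordinal models.

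**The case against.** The strongest reply is that randomisation within cohort already protects the comparison. Step 3 bears this out: with complete data the estimate is unbiased and the test errs on the safe side. In the mixed models the random intercept also absorbs any stable difference between series, so only series-by-time change matters. Every size above rests on an assumed shift, and a 3% gain in standard error is not large. All of this stands.

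Several stronger readings are tempting and are not supported:

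- *Every model in the SAP adjusts only for site and sex.* Aim 3 conditions on pre-treatment covariates, with confirmatory models for potential confounders, and Aim 4 adds moderators.
- *One curve is forced on all families.* The treatment-by-time term gives each arm its own; the curve is common only across series.
- *Cohort 1 is before the pandemic and cohort 2 after.* Wisconsin cohort 1 ran alongside cohort 2 in Tennessee and Illinois. No baseline dates are given, and the note on moving testing online speaks of remaining participants, not of a cohort.
- *A 10-point arm difference in cohort mix gives 0.05 SD of bias at a 0.5 SD shift.* The shift belongs to 60 of the 90 cohort 1 families. If loss is proportional within cohort, 10 points of cohort mix is about 6.7 points of early-series share, and 0.067 × 0.5 = 0.033 SD. Nothing in the documents suggests such a differential loss.

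The SAP also plans a dropout model on all baseline predictors. That might reveal a link with series, but the SAP states no action to follow.

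Finally, a full set of series-by-visit terms would be too heavy: 5 × 2 = 10 further d.f. for T0, T2 and T3, or 5 × 4 = 20 for T0, T2, T3, T5 and T6. That leaves about 152/12 ≈ 13 retained families per arm per series in logistic and ordinal GEE, and it does not match the spline time scale. This objection stands and limits the fix.

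**Conclusion.** The point holds as a modest improvement to the Aim 1, 2, 2a and 2b models. A factor used in the allocation is missing from them, and one third of families had a different calendar and a stretched intervention period that the common time curve cannot represent.

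The cost is a standard error larger than it need be: the achievable reduction is about 1%, 3% or 6% for assumed shifts of 0.3, 0.5 or 0.8 SD. Bias is conditional on dropout related to series differently by arm. At a 0.5 SD shift it is about 0.05 SD in a pattern already improbable by chance, and 0.09 SD at the limit, against a detectable difference of 0.46 SD. The GEE outcomes (employment or post-secondary education, number of services) are the most exposed, because the SAP assumes their data are missing completely at random.

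A reader should not infer that the planned analysis is invalid or anti-conservative; without differential loss the reverse is true. The conclusion assumes that blocks were formed separately in each cohort at each site, which is the natural reading of Protocol section 4, and that the early baselines predate the shutdown, which follows from the workshop dates.

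**What to change.** In the Aim 1, 2, 2a and 2b models, and in Protocol section 8 to match:

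1. Replace site (2 d.f.) with the six-level site-by-cohort series (5 d.f.).
2. Add one indicator for Tennessee and Illinois cohort 1, interacted with the model's time terms. Its main effect is already contained in series. It should not be crossed with treatment, so a single treatment-by-time contrast remains.
3. Keep fuller series-by-time terms as a sensitivity analysis for the continuous outcomes only.

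The cost is SAP wording, 3 extra main-effect d.f., and as many interaction d.f. as the time spline has. The SAP does not state the number of knots; with an assumed three to five, that is 2 to 4. This is small against about 152 families. No new data are needed.
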